Briefly, patients will undergo baseline eligibility screening within 2 weeks prior to enrollment, including a medical history, physical examination, and assessment of performance status and hematology and chemistry parameters. Baseline assessment of disease status will be based on results of a bone marrow aspirate and biopsy for patients with AML and MDS, and a CT/PET scan (with a bone marrow exam for history of disease involvement) for patients with lymphoma. Baseline and subsequent bone marrow and peripheral blood samples will be obtained for correlative assays. Disease response assessment (bone marrow aspirate and biopsy and/or CT/PET) will be performed at baseline, and then every 3 months for 2 years, as well as any time if relapse is suspected. Specific procedures to be performed during the trial, as well as their prescribed times and associated visit windows, are outlined in the trial flow chart – Section 7.0. Details of each procedure are provided in Section 8.0 – trial procedures. After 24 months, ongoing disease re-assessments will be performed at the discretion of the treating physician. Any patient who experiences biopsy-proven disease progression at any time will be removed from study, and alternative treatment can be recommended at the treating physician's discretion. Subjects are not eligible for re-treatment on with pembrolizumab in the setting of this protocol should they experience a disease relapse after completing 24 months of therapy. After the end of treatment, each subject will be followed for 30 days for adverse event monitoring (serious adverse events will be collected for 90 days after the end of treatment). Subjects who discontinue treatment for reasons other than disease progression will have post-treatment follow-up for disease status until disease progression, initiating a non-study cancer treatment, withdrawal of consent, or becoming lost to follow-up. All subjects will be followed by telephone contact for overall survival until death, withdrawal of consent or the end of the study, whichever comes first.

The primary objective of this trial is to determine whether administration of pembrolizumab is tolerable in patients who have experienced disease relapse following alloSCT. Secondary objectives include analysis of efficacy parameters (ORR, DOR, OS). Correlative studies to examine the effect of PD-1 blockade therapy on T cell parameters and clonality, as well as on donor chimerism are planned as exploratory analyses.

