3.2 SECONDARY OBJECTIVES & HYPOTHESES

Objective 1: To determine the overall response rate (ORR) of patients treated with pembrolizumab in the setting of relapsed myeloid malignancies and mature B cell lymphomas following alloSCT, stratified by disease type. ORR is defined as the first documentation of CR or PR (by IRC) to the first documentation of disease progression or death by any cause.

Objective 2: To determine the duration of response (DOR) of patients treated with pembrolizumab in the setting of relapsed myeloid malignancies and mature B cell lymphomas following alloSCT. DOR is defined as the time between the initial response to therapy and subsequent disease progression or relapse.

Objective 3: To determine the overall survival (OS) of patients treated with pembrolizumab in the setting of relapsed myeloid malignancies and mature B cell lymphomas following alloSCT. OS is defined as the interval from the start of the study treatment to death from any cause.

Hypothesis 1: Pembrolizumab will have anti-tumor activity in the defined patient population as measured by ORR.

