explore if the chosen pembrolizumab dose and schedule (i.e. 200 mg Q3W) is safe in this patient population.

5.4 RATIONALE FOR EFFICACY ENDPOINTS.

The secondary objective of this study (primary efficacy endpoints) is to determine the anti-tumor activity of pembrolizumab treatment in subjects with relapsed AML, MDS or mature B cell lymphomas following alloSCT. The overall response rate (ORR) will be the most valuable and primary efficacy endpoint. ORR for B cell lymphoma patients will be assessed according to the International Working Group criteria³⁹. ORR for AML and MDS patients will be assessed according to the European Leukemia Net and International Working Group response criteria, respectively^{40, 41}. ORR is defined as the proportion of subjects who achieve an objective disease response, as defined in Section 3.2.

Secondary efficacy endpoints include duration of response (DOR) and overall survival (OS). DOR is defined as the interval from the first documentation of an objective disease response, as defined in Section 3.2, to the documentation of disease progression, as defined in Section 3.2. OS is defined as the interval from the date of study enrollment to death from any cause.

5.5 RATIONALE FOR BIOMARKER RESEARCH.

Effect of pembrolizumab treatment on restoring donor chimerism. Disease relapse following alloSCT is commonly associated with a decline in donor chimerism. By stimulating donor-derived T cells, it is hypothesized that pembrolizumab will improve or even completely restore full donor chimerism in patients with relapsed disease after alloSCT (where loss or decline in donor chimerism has been documented to occur). Donor chimerism in both the entire WBC population and in the CD3+ cell compartment will be analyzed by short tandem repeat analysis on 10 pre-defined loci by PCR and a capillary amplifier. Analyses on peripheral blood (all patients) and bone marrow aspirates (in AML and MDS patients only) will be performed at baseline (pre-treatment) and at 3, 6, 9, 12, 15, 18, 21 and 24 months of pembrolizumab treatment. It is expected that pembrolizumab treatment will improve or completely restore donor chimerism in treated patients. A correlation between donor chimerism status and objective response will be sought, although patient number may be too small to make any definitive conclusion.

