8.1.5.1 SCREENING

Approximately 28 days prior to start of study drug dosing, potential subjects will be evaluated to determine that they fulfill the entry requirements as set forth in Section 6.1. Screening procedures may be repeated after consultation with the principal investigator.

Written consent for the main study must be obtained prior to performing any protocol specific procedure. Results of a test performed prior to the subject signing consent as part of routine clinical management are acceptable in lieu of a screening test if performed within the specified time frame. Screening procedures are to be completed within 28 days prior to the first dose of trial treatment except for the following:

Laboratory tests are to be performed within 10 days prior to the first dose of trial treatment.

For women of reproductive potential, a urine pregnancy test will be performed within 72 hours prior to the first dose of trial treatment. If urine pregnancy results cannot be confirmed as negative, a serum pregnancy test will be required (performed by the local study site laboratory).

Subjects may be rescreened after initially failing to meet the inclusion/exclusion criteria. Results from assessments performed during the initial screening period are acceptable in lieu of a repeat screening test if performed within the specified time frame and the inclusion/exclusion criteria is met.

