9.1.2 EFFICACY ANALYSES

The intention-to-treat population, defined as subjects who received at least one dose of pembrolizumab, will serve as the primary analysis population in this study. The primary efficacy endpoint is the overall response rate (ORR), defined as those patients who achieve a PR or CR (lymphoma), PR or CR (MDS), or a CR, CRp, CRi or PR (AML). Secondary efficacy endpoints include duration of response (DOR) and overall survival (OS).

An outline of the efficacy analysis strategy is shown in Table 12 below.

Table 12. Primary analysis strategy for efficacy endpoints

Endpoint/Variable (Description, Time Point)	Statistical Method	Analysis Population	Missing Data Approach
Primary:			
Overall response rate (ORR) using defined criteria	Exact test of binomial parameter	ITT	Subjects with missing data are considered non-responders
Secondary:			
Duration of response (DOR)	Summary statistics using Kaplan-Meier method	All responders	Non-responders are excluded in analysis
Overall survival (OS)	Summary statistics using Kaplan-Meier method	ITT	Censored at last assessment

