9.2.3.2 EFFICACY ANALYSIS POPULATION

The analysis of primary efficacy endpoints are based on the intention-to-treat (ITT) population, i.e., subjects will be included if they receive at least one dose of study medication.

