9.2.4.2.3 OVERALL SURVIVAL (OS)

OS will be summarized using a Kaplan-Meier survival curve.

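### Overall survival starts at first treatment in Section 3.2 but at enrollment in Section 5.4; because Table 12 analyses OS in dosed subjects only, the enrollment origin would add a usually small stretch of guaranteed survival.

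*Combined protocol and SAP*

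**What the plan says.** Two current sections define the same endpoint. Section 3.2, under Objective 3, has "OS is defined as the interval from the start of the study treatment to death from any cause". Section 5.4, on the rationale for the efficacy endpoints, has "OS is defined as the interval from the date of study enrollment to death from any cause".

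The analysis sections do not choose between them. Section 9.2.4.2.3 says only that "OS will be summarized using a Kaplan-Meier survival curve". In Section 9.1.2, the OS row of Table 12 gives the Kaplan-Meier method, the ITT population and the rule "Censored at last assessment", but no starting date. Section 9.2.1 refers the reader to Section 3 for objectives and hypotheses.

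The label ITT has a particular meaning here. Section 9.1.2 has "The intention-to-treat population, defined as subjects who received at least one dose of pembrolizumab". Section 9.2.3.2 repeats the one-dose condition ("subjects will be included if they receive at least one dose of study medication"), but its sentence is about the primary efficacy endpoints. OS is secondary, so it is Table 12 that ties OS to the dosed-only population.

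**The concern.** A starting date for survival has to match the rule for entering the analysis. Subjects enter this OS analysis by receiving a dose. Anyone who enrolls and dies before dosing is left out, and everyone who is included was alive throughout the interval from enrollment to first dose. If the clock starts at enrollment, that interval counts as survival although no included subject could have died in it. The bias has one direction: OS can only look longer.

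The mismatch is therefore more than editorial. With this population the Section 3.2 origin is unbiased in this respect and the Section 5.4 origin is not, yet an analyst could cite the protocol for either. If the choice is left open, it could also be made after the data have been seen.

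**Working it through.** **No planned figure to reproduce.** The documents give no expected median OS, no OS event count and no enrollment-to-dose interval. The sizes below are for scale and rest on stated assumptions.

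**What bounds the gap**
- Section 2.1: "patients will undergo baseline eligibility screening within 2 weeks prior to enrollment". Enrollment therefore follows screening.
- Section 8.1.5.1: "Screening procedures are to be completed within 28 days prior to the first dose of trial treatment". The flow chart in 7.1 shows the same window, Day -28 to -1. These 28 days run from screening to dose, not from enrollment to dose.
- Sections 6.1.2, 8.1.3.1 and 8.1.5.1: screening laboratory tests fall within 10 days of first dose. If enrollment follows confirmed eligibility and the tests are not repeated, the gap is about 0 to 10 days.
- No section defines the enrollment date. A gap of 28 days would require it to mean consent or the start of screening.

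**Which medians to try**
- 4 and 6 months: assumed. Section 4.1 describes the prognosis of aggressive cancers relapsing after transplant as very poor.
- About 11 months: derived from the 2-year survival of 21% after donor lymphocyte infusion in Section 4.4, assuming exponential survival: 24 × ln 2 / (−ln 0.21) = 24 × 0.693 / 1.561 = 10.7 months.

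**Formula.** With a constant gap g, survival at time t from enrollment equals survival at t − g from first dose. The median rises by exactly g, so inflation = g / median. With 30.44 days to the month, 10 days is 0.33 months and 28 days is 0.92 months.

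| Assumed gap | Median 4 months | Median 6 months | Median 10.7 months |
|---|---|---|---|
| 0 days | 0% | 0% | 0% |
| 10 days | 0.33/4 = 8.2% | 0.33/6 = 5.5% | 0.33/10.7 = 3.1% |
| 28 days | 0.92/4 = 23.0% | 0.92/6 = 15.3% | 0.92/10.7 = 8.6% |

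**On the probability scale.** With exponential survival and a 6-month median, 6-month OS from first dose is 50.0%. From enrollment it becomes 0.5 × 2^(0.33/6) = 51.9% at 10 days and 0.5 × 2^(0.92/6) = 55.6% at 28 days. For comparison, the standard error of a 50% estimate in 26 subjects without censoring is √(0.25/26) = 9.8 percentage points.

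**With first dose as the origin** the guaranteed time is zero by construction, whatever the gap.

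**The case against.** The best defence is that the plan already points to the right answer. Section 9.2.1 sends the reader to Section 3, where OS starts at treatment. Section 5.4 is a rationale section that itself defers to 3.2 for response and its duration. On that view the enrollment wording is a stray phrase that nobody would program from. Much of this stands: treatment start is the likelier reading. But 9.2.1 refers to objectives and hypotheses and does not withdraw 5.4, which writes out its own OS definition instead of deferring to 3.2.

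The second defence is about size, and it largely stands. A reader might take the 28-day screening window as the enrollment-to-dose gap, pair gaps of two to four weeks with a 4-month median, and conclude that OS is inflated by 11 to 23% (0.46/4 to 0.92/4). The documents do not support that as the expected effect. The window is measured from screening, enrollment comes after screening, and the 10-day laboratory rule suggests a shorter gap, possibly none. Nor does the poor prognosis in Section 4.1 describe the whole cohort: it concerns aggressive cancers, while Section 6.1.2 admits any mature B cell lymphoma, requires ECOG 0-1 and requires more than 90 days since transplant.

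Third, no decision depends on OS. The stopping and expansion rules in 9.1.1, 9.1.3 and 9.2.4.1 count DLTs, and the plan sets no OS test, comparator or threshold. This is correct and limits the importance of the point.

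**Conclusion.** The contradiction between 3.2 and 5.4 is certain, and so is the direction of the bias if 5.4 is followed in the Table 12 population. The size is uncertain and probably modest: 0 to 8% of the median for assumed gaps of 0 to 10 days and assumed medians of 4 to about 11 months. It reaches 9 to 23% only if enrollment means consent or the start of screening and the gap is the full 28 days. The effect vanishes for anyone dosed on the day of enrollment. These figures assume a constant gap; with varying gaps, each subject gains his or her own.

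A reader might also infer that the reported OS will be biased, or that the trial's conclusion on tolerability is at risk. Neither follows. The plan may well be carried out under the 3.2 definition, and the DLT decision rules, alpha and power do not use OS. This is a minor point, worth correcting because the correction costs almost nothing.

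**What to change.** In Section 5.4, change the OS origin from enrollment to the start of study treatment, specified as the first dose of pembrolizumab, so that it agrees with 3.2. State the same origin in 9.2.4.2.3, so that the analysis section stands on its own.

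The cost is one phrase and one added sentence, and reported OS may be slightly shorter than under the 5.4 wording. If the sponsor prefers to count from enrollment, the population must change with it: either include every enrolled subject, dosed or not, or let subjects enter the risk set at first dose (delayed entry). Either is a larger change than aligning 5.4 with 3.2.

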3.3 EXPLORATORY OBJECTIVES & HYPOTHESES

Objective 1: To determine the effect of pembrolizumab on restoring donor chimerism in patients with relapsed myeloid malignancies and mature B cell lymphomas following alloSCT.

Objective 2: To determine the effect of pembrolizumab on the numbers and activations status of peripheral blood T cells.

Objective 3: To compare PD-L1 expression on malignant cells at initial diagnosis and at disease relapse following alloSCT.

Objective 4: To examine the effect of pembrolizumab on the T cell receptor (TCR) repertoire in the peripheral blood, and where available, tumor environment, following alloSCT.

Hypothesis 1: Pembrolizumab treatment will restore donor chimerism when administered to patients with relapsed myeloid malignancies and mature B cell lymphomas following alloSCT.

Hypothesis 2: Pembrolizumab treatment will be associated with enhanced expression of activation markers on peripheral blood T cells in patients with relapsed myeloid malignancies and mature B cell lymphomas following alloSCT.

Hypothesis 3: PD-L1 expression will be increased on malignant cells following disease relapse after alloSCT compared to diagnosis.

Hypothesis 4: Pembrolizumab treatment will be associated with clonal expansion of conventional and regulatory T cell subsets in peripheral blood as measured by TCR- β deep sequencing and Simpson's index of diversity analysis.

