Effect of pembrolizumab on T cell number and activation status. Pembrolizumab, by interrupting PD-1/PD-L1 interactions, may affect not only numbers of T cells present in peripheral blood (and bone marrow), but may also lead to upregulation of activation markers on peripheral blood T cells. To explore this hypothesis, the frequencies and absolute numbers of T cell subsets (conventional CD4+ and CD8+ and CD4+CD25+CD127- regulatory T cells (Tregs)) will be enumerated in the peripheral blood (all patients) and bone marrow (AML and MDS patients only) at several defined time points prior to and following pembrolizumab treatment (pre-treatment, and at 3, 6, 9, 12, 15, 18, and 24 months of treatment). Peripheral blood mononuclear cells (PBMC) or bone marrow cells will be stained with anti-CD3, anti-CD8, anti-CD4, anti-CD25, and

anti-CD127 antibodies and analyzed by flow cytometry to define specific T cell subsets. Conventional CD4+ T cells will be defined as CD3+CD4+CD25-/low cells, while conventional CD8+ T cells will be defined as CD3+CD8+ cells. Tregs will be defined as CD3+CD4+CD25hiCD127- cells. Frequencies will be calculated by sub-gating on the lymphocyte population as appropriate. Absolute numbers of T cells in each subset will be enumerated by multiplying the frequency of each T cell subset by the total white blood count from each sample. T cell activation status will be analyzed by co-staining cells with antibodies directed against the following markers: HLA-DR, CD69, ICOS and CD25 (others may be added). Descriptive statistics will be utilized to compare pre- and post-treatment frequencies, absolute numbers and activation status of T cells in enrolled patients. The goal would be to define potential biomarkers associated with responsiveness to pembrolizumab treatment that could be verified in larger studies in a similar patient population.

Detection of PD-L1 and PD-L2 expression. To determine whether expression of PD-1 ligands on malignant or non-malignant cells in the tumor environment may be a driver of disease relapse following alloSCT, PD-L1 and PD-L2 expression will be analyzed and compared between diagnostic samples and post-alloSCT relapse samples. This assay will be performed in collaboration with Merck using in-house protocols.

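### The CD25-/low gate drops conventional CD4 cells that become CD25-high, which biases the pre/post count downward and caps CD25 as an activation readout in that subset

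*Combined protocol and SAP*

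**What the plan says.** Section 3.3 sets exploratory objective 2, the effect of pembrolizumab on T cell numbers and activation status in peripheral blood. Its hypothesis is that treatment goes with "enhanced expression of activation markers on peripheral blood T cells". No subset is named.

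Section 5.5 gives the method:

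- Conventional CD4: "Conventional CD4+ T cells will be defined as CD3+CD4+CD25-/low cells". CD127 plays no part in this gate.
- Tregs: "Tregs will be defined as CD3+CD4+CD25hiCD127- cells". Earlier in the same paragraph they appear as "CD4+CD25+CD127- regulatory T cells (Tregs"), so the CD25 requirement is written two ways.
- CD8: "conventional CD8+ T cells will be defined as CD3+CD8+ cells", with no CD25 condition.
- Activation: co-staining for "HLA-DR, CD69, ICOS and CD25 (others may be added"). The paragraph does not say whether these are read on all CD3+ cells, on all CD4+ cells or inside each subset gate.
- Absolute numbers: obtained by "multiplying the frequency of each T cell subset by the total white blood count".

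Frequencies, absolute numbers and activation status are then compared descriptively before and after treatment.

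**The concern.** A subset definition should not depend on the quantity that treatment is expected to change. Here it does: the hypothesised effect, activation, includes a rise in CD25, and a rise in CD25 beyond low takes a cell out of the conventional CD4 gate. The resulting error differs between the pre-treatment and post-treatment samples, so it does not cancel in the comparison. Because absolute numbers are built from subset frequency, the loss carries into them as well.

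What is at stake is the reading of exploratory objective 2 and the stated aim of finding candidate biomarkers to verify in larger studies. A fall in conventional CD4 cells could be reported when cells have only changed label, and a subset definition with this property could be carried into later work.

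**Working it through.** The plan gives no expected value, power or sample size for this readout, so there is no figure to reproduce. The check is a count of which cells fall in which gate.

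**Step 1: classification of CD3+CD4+ cells under the definition sentences of section 5.5**

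| CD25 | CD127 | Subset |
|---|---|---|
| negative or low | either | conventional CD4 |
| high | negative | Treg |
| high | positive | none |

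The two CD4 gates do not cover all CD4 cells. Within conventional CD4 the CD25-high share is zero by construction, before and after treatment. Within Tregs CD25 is always high. A move from negative to low can still be seen inside the conventional gate; a move above the cut cannot. The documents do not define the cut.

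**Step 2: effect on the count**

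Inputs, all assumed because the documents supply none: N = 1000 non-Treg CD4 cells; a = activated share, rising from 5% to 20%; e = share of activated cells whose CD25 passes the gate limit, from 0.25 to 1.

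- Gated count = N(1 − ae).
- Break-even true growth, below which the gated count falls = (1 − 0.05e)/(1 − 0.20e) − 1.

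For e = 0.5: before, 1000 × (1 − 0.025) = 975; after, 1000 × (1 − 0.10) = 900; change −7.7%; break-even 0.975/0.90 − 1 = 8.3%.

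| e | Gated count, N fixed | Change | Break-even true growth | Change if true growth is 20% |
|---|---|---|---|---|
| 0.25 | 987.5 to 950.0 | −3.8% | 3.9% | +15.4% |
| 0.50 | 975.0 to 900.0 | −7.7% | 8.3% | +10.8% |
| 0.75 | 962.5 to 850.0 | −11.7% | 13.2% | +6.0% |
| 1.00 | 950.0 to 800.0 | −15.8% | 18.75% | +1.1% |

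With a smaller rise in a, from 5% to 10%, and N fixed, the falls are 1.3%, 2.6%, 3.9% and 5.3%.

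**Step 3: HLA-DR, CD69 and ICOS, if read inside the gate**

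In-gate activated share = a(1 − e)/(1 − ae).

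| e | In-gate share | Rise in points (true rise 15) |
|---|---|---|
| 0.25 | 3.8% to 15.8% | 12.0 |
| 0.50 | 2.6% to 11.1% | 8.5 |
| 0.75 | 1.3% to 5.9% | 4.6 |
| 1.00 | 0% to 0% | 0 |

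At constant e below 1 the derivative in a is (1 − e)/(1 − ae)², which is positive, so the readout rises with activation. The attenuation is in level and in percentage points. The after/before ratio is not reduced: at e = 0.5 it is 11.11/2.56 = 4.3, against a true 4. A reversal needs e to rise as well: with a from 5% to 10% and e from 0.25 to 0.75 the in-gate share goes from 3.8% to 2.7%, but with a from 5% to 20% and the same change in e it goes from 3.8% to 5.9%.

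**Step 4: with conventional CD4 defined as everything outside the Treg gate**

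With N fixed, the count reads 1000 to 1000 and activation 5% to 20%, provided none of the escaping cells are CD127-negative.

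**The case against.** The strongest reply is that section 5.5 names no parent population for activation, and the hypothesis in section 3.3 concerns peripheral blood T cells in general. If the four markers are read on all CD3+ or all CD4+ cells, no activated cell is lost from that readout. This stands. It means a reader who infers that the activation result will move the wrong way, or that the plan as written yields a false negative for hypothesis 2, goes beyond the documents. Even inside the gate the other three markers are generally attenuated, and CD25 is capped; neither is reversed as a rule.

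Other points also stand. Cells with low CD25 stay in the gate, so the case in which every activated cell escapes is an extreme. Section 5.5 itself expects that T cell numbers may change, and enough true growth keeps the direction of the count right. A reader might infer that CD4 and CD8 results are made non-comparable, but the plan compares pre with post and announces no CD4-versus-CD8 comparison. Nothing in the documents shows that the cells lost are those richest in HLA-DR, CD69 or ICOS.

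None of this rescues the conventional CD4 frequency and count, because the written definition fixes that gate.

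**Conclusion.** The concern holds in a limited form. Using CD25 as both gate and marker introduces a treatment-dependent downward bias in the conventional CD4 frequency and count, leaves CD25-high CD127+ cells unclassified, and prevents CD25 from showing activation above the cut in that subset. The size is unknown. About 4% to 16% is an illustration that rests on an assumed rise in activation from 5% to 20%, no true change in cell number and an escape share of 25% to 100%. The direction of the count is wrong only when true expansion is smaller than the gate loss, that is, below about 4% to 19% over the same range.

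CD8 readouts are unaffected, as is CD4 activation read on all CD4+ or CD3+ cells. The consequence is confined to a descriptive exploratory objective in a pilot of 12 to 26 patients; no primary or secondary endpoint depends on it.

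**What to change.** In section 5.5:

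1. Give one Treg definition, reconciling the CD25+ and CD25hi wordings, and state how the CD25 cut is set.
2. Gate Tregs first and define conventional CD4 as all remaining CD3+CD4+ cells.
3. State that CD25, HLA-DR, CD69 and ICOS are read on that population and on CD8 cells.

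The cost is close to nil. The antibodies needed for gating (CD3, CD4, CD8, CD25, CD127) are already in the panel, and only the definition changes. Samples already analysed could be re-gated if the flow files were kept, which the documents do not say.

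Two limitations remain. Activated cells that are CD25-high and CD127-negative would still be counted as Tregs. If the CD25hi wording is kept, any Tregs below that cut would be counted as conventional, as those with CD25-/low already are under the present gate.

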6.1.2 SUBJECT INCLUSION CRITERIA

1. Signed written informed consent

- a) Subjects must have signed and dated an IRB-approved written informed consent form in accordance with regulatory and institutional guidelines. This must be obtained before the performance of any protocol-related procedures that are not part of normal subject care.

- b) Subjects must be willing and able to comply with scheduled visits, treatment schedule, laboratory tests and other requirements of the study.

2. Target population

- a) Subjects must be ≥ 18 years of age.
- b) Subjects must have an ECOG performance status of 0-1 (Appendix).
- c) Subjects have undergone alloSCT > 90 days prior to enrollment from a matched-related donor (MRD), matched-unrelated donor (MUD), cord blood donor, or haplo-identical and cord blood donor.
- d) There must be histological confirmation of relapse after alloSCT of any of the following diseases: any mature B cell lymphoma (cHL or NHL), AML or MDS.
- e) Subjects must be off of all immunosuppressive medications for a minimum of 2 weeks with the exception of physiologic doses of corticosteroids.
- f) Subjects with B cell lymphoma must have measurable disease, defined as at least 1 lesion that can be accurately measured in at least 2 dimensions with CT scan. Minimum measurement must be > 15 mm in the longest diameter and > 10 mm in the short axis.
- g) Subjects must not have had any prior investigational agents or devices within 4 weeks of beginning study drug
- h) Subjects must have no prior history of VOD
- i) Subjects must demonstrate adequate organ function as defined in **Table 2**. All screening labs should be performed within 10 days of treatment initiation.

Table 2. Adequate Organ Function Laboratory Values

System	Laboratory Value
Hematological	
Absolute neutrophil count (ANC)	≥ 500 /mCL
Platelets	$\geq 20,000$ /mCL
Hemoglobin	≥ 8 g/dL (RBC transfusions are OK)
Renal	
Serum creatinine OR Measured or calculated ^a creatinine clearance (GFR can also be used in place of creatinine or	≤ 1.5 X upper limit of normal (ULN) or ≥ 60 mL/min for subject with creatinine levels > 1.5 X institutional ULN

CrCl)	
Hepatic	
Serum total bilirubin	$\leq 1.5 \times \text{ULN}$ or direct bilirubin $\leq \text{ULN}$ for subjects with total bilirubin levels $> 1.5 \times \text{ULN}$
AST (SGOT) and ALT (SGPT)	$\leq 2.5 \times \text{ULN}$
Albumin	$\geq 2.0 \text{ mg/dL}$
Coagulation	

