12.5.1 COMPLETE REMISSION (CR)

Bone marrow evaluation: Bone marrow showing < 5% myeloblasts with normal maturation of all cell lines, with no evidence for dysplasia (see dysplasia qualifier under peripheral blood evaluation). When erythroid precursors constitute < 50% of bone marrow nucleated cells, the percent of blasts is based on all nucleated cells; when there are \geq 50% erythroid cells, the percent blasts should be based on the non-erythroid cells.

- Peripheral Blood Counts (Absolute values must last \geq 8 weeks).
- Hemoglobin greater than 11 g/dL.
- Neutrophils 1500/mm³ or more (not on a myeloid growth factor).
- Platelets 100 000/mm³ or more (not on a thrombopoietic agent).
- Blasts \leq 5%.
- No dysplasia. The presence of mild megaloblastoid changes may be permitted if they are thought to be consistent with treatment effect. However, persistence of pretreatment abnormalities (e.g., pseudo-Pelger Huet cells, ringed sideroblasts, dysplastic megakaryocytes) is not consistent with CR.

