12.5.2 PARTIAL REMISSION (PR)

- All of the CR criteria (if abnormal prior to treatment), except:
- Bone marrow evaluation: Blasts decreased by 50% over pretreatment, or a less advanced MDS WHO classification than pretreatment. Cellularity and morphology are not relevant.

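### Section 5.5 multiplies a lymphocyte-gate T-cell frequency by total WBC, so absolute blood counts are overstated by WBC/ALC and can shift when T cells have not changed

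*Combined protocol and SAP*

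**What the plan says.** Exploratory Objective 2 in Section 3.3 is "To determine the effect of pembrolizumab on the numbers and activations status of peripheral blood T cells". Section 5.5 describes the assay in this order:

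- Material: "Peripheral blood mononuclear cells (PBMC) or bone marrow cells will be stained with" antibodies that define the T-cell subsets.
- Denominator: "Frequencies will be calculated by sub-gating on the lymphocyte population as appropriate".
- Absolute numbers, in the sentence after that: "enumerated by multiplying the frequency of each T cell subset by the total white blood count from each sample".
- Use: "Descriptive statistics will be utilized to compare pre- and post-treatment frequencies, absolute numbers and activation status of T cells in enrolled patients". The stated goal is to find candidate markers of responsiveness for checking in larger studies.

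No step in Section 5.5 or elsewhere converts a share of lymphocytes into a share of all white cells.

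**The concern.** A frequency gives an absolute count only when it is multiplied by the count of the population it is a share of. Here the share is of lymphocytes and the multiplier is all white cells.

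A constant error in level would matter little for a within-patient comparison. The difficulty is that WBC/ALC need not be constant, least of all in AML and MDS, where neutrophils and blasts form part of the response definition. Table 2 (Section 6.1.2) admits patients with a neutrophil count of 500. MDS complete remission (Section 12.5.1) needs 1500/mm3 "or more (not on a myeloid growth factor"), and partial remission (Section 12.5.2) carries this over: "All of the CR criteria (if abnormal prior to treatment), except" for the marrow finding. WBC/ALC can therefore move because of the response itself. A T-cell count computed by this rule could then appear linked to response when the T cells have not changed.

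**Working it through.** The plan states no figure on this point, so there is nothing to reproduce. The check is algebra on the written rule, followed by illustrations. Counts are in 10^9/L.

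**Algebra.** Let T be the true subset count in blood.

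- Rule as written: (T/ALC) x WBC = T x (WBC/ALC).
- Matched rule: (T/ALC) x ALC = T.
- Overstatement: WBC/ALC = 1/f, where f is the lymphocyte fraction of WBC.

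**Size by lymphocyte fraction (f assumed).**

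| f | 10% | 20% | 40% | 50% | 60% | 80% |
|---|---|---|---|---|---|---|
| 1/f | 10 | 5 | 2.5 | 2 | 1.67 | 1.25 |

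**False rise.** The neutrophil values are the protocol's: 0.5 (entry floor) and 1.5 (MDS response threshold). ALC is assumed and constant, T cells are unchanged, and WBC is taken as ALC + ANC, ignoring monocytes and blasts. The apparent fold change is (ALC + 1.5)/(ALC + 0.5):

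- ALC 0.3: 1.8/0.8 = 2.25
- ALC 0.8: 2.3/1.3 = 1.77
- ALC 2.0: 3.5/2.5 = 1.40

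For instance, take CD8 cells at 30% of lymphocytes with ALC 0.8. The true count is 0.30 x 0.8 = 0.24 at both visits. The rule gives 0.30 x 1.3 = 0.39, then 0.30 x 2.3 = 0.69.

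**False fall (all values assumed).** Blasts clear and WBC goes from 6 to 2, with ALC constant at 0.8. The true count stays at 0.24. The rule gives 0.30 x 6 = 1.8, then 0.30 x 2 = 0.6, an apparent fall to one third.

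**Hidden rise (all values assumed).** ALC goes from 0.8 to 1.6 while WBC goes from 6 to 3. The true count doubles, from 0.24 to 0.48. The rule gives 1.8, then 0.30 x 3 = 0.9, a halving.

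**Other readings of the text.**

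- Frequency as a share of all PBMC: the ratio becomes WBC/(lymphocytes + monocytes). With assumed ALC 1.0 and monocytes 0.3 it is 3/1.3 = 2.31 at WBC 3 and 6/1.3 = 4.62 at WBC 6. With monocytes 0.6 it is 6/1.6 = 3.75 at WBC 6. PBMC preparations largely exclude granulocytes, so the mismatch with total WBC remains.
- Frequency on a narrower parent, such as regulatory T cells as a share of CD4+ cells: the overstatement is larger.
- White count of the processed sample: this gives cells per sample. A blood concentration would also need the processed volume and the recovery, and neither is stated.
- Bone marrow: the same sentence covers marrow but names no matching denominator and multiplier.

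**The case against.** The strongest reply is about weight. The endpoint is exploratory and descriptive. Hypothesis 2 in Section 3.3 concerns activation markers, not counts, and no test, threshold or decision in Section 9 uses the absolute numbers. With 12 to 26 patients across several diseases, nothing definitive would be drawn from them. The blood error is also recoverable: if gate frequencies are kept, counts can be recomputed from the ALC without new samples. All of this stands and limits the importance of the point. It does not make the rule correct, and recovery depends on someone noticing.

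A second reply is that the gating is to be done as appropriate and the parent population of each subset is never stated, so the denominator is not fully fixed. That is true, but the lymphocyte gate is the only denominator named, and a PBMC denominator fails too.

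Third, the factor is exactly WBC/ALC only if the cytometry gate and the haematology lymphocyte count describe the same cells. Circulating blasts or lymphoma cells in the gate make it approximate, and they make a count based on ALC approximate as well. This stands as a caveat on both the size and the fix.

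Fourth, the illustrations show what can happen, not what is expected. Only the two neutrophil limits come from the protocol, and they are a floor and a threshold rather than typical values. This also stands.

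**Conclusion.** The rule is wrong as written. Followed literally, it overstates absolute T-cell counts in blood by about WBC/ALC: 10-fold to 1.25-fold over an assumed lymphocyte fraction of 10% to 80%. Fold changes within a patient are right only if WBC/ALC is constant; otherwise the error can create, reverse or hide a change. The risk is greatest in AML and MDS. The sizes rest on assumed lymphocyte, white cell and blast counts, and on the cytometry gate matching the haematology ALC.

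The effect is confined to the absolute numbers reported under Exploratory Objective 2. Subset frequencies, activation markers, DLT, ORR, DOR and OS are untouched. The sentence should be corrected before absolute counts are analysed.

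**What to change.** Replace the enumeration sentence in Section 5.5 with:

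> In peripheral blood, the absolute number of each subset is its frequency as a share of lymphocytes multiplied by the absolute lymphocyte count from the CBC differential closest to the correlative sample (same day where available; both dates recorded). In bone marrow, the frequency is expressed as a share of all nucleated cells and multiplied by the nucleated cell count of that sample; if no such count is taken, frequencies are reported.

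This fixes one denominator for every blood subset. Where blasts or lymphoma cells may fall in the lymphocyte gate, the report should say that the count is approximate.

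For blood the cost is a text change with no extra draw: ALC is in Table 10 (Section 8.1.3.1), and the Section 7 flow charts schedule a CBC with differential at screening and at every correlative visit. One small downside is that the two samples may fall on different days, since pre-dose laboratory tests after cycle 1 may be drawn up to 72 hours before dosing and screening tests up to 10 days before the first dose. For marrow, an absolute number needs a nucleated cell count if none is taken now; reporting frequencies avoids any new procedure.
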